9.8 Analysis of the Primary PD Endpoint (WBCT)

Definition of Reversal of Anticoagulation

- Complete reversal is achieved for a treatment group if the mean WBCT is $\leq 110\%$ of baseline at any post-baseline time point up to and including 1 hour following test article administration. Complete reversal is achieved for a subject if WBCT is $\leq 110\%$ of baseline at any post-baseline time point up to and including 1 hour following test article administration.
- Complete and sustained reversal of anti-coagulation is achieved for a treatment group if the mean WBCT is $\leq 115\%$ of baseline at all time points between 1 and 8 hours (inclusive) following test article administration. Complete and sustained reversal of anti-coagulation is achieved for a subject if WBCT is $\leq 115\%$ of baseline at all time points between 1 and 8 hours (inclusive) following test article administration.

Statistically Significant Complete Reversal

- Statistically significant complete reversal, relative to mean placebo WBCT, is defined as $p < 0.05$, (one tailed) from the comparison of means between treatment and placebo at 15, 30, 45 minutes or 1 hour post study drug administration as measured by one-way Analysis of Variance at study completion. Distribution diagnostics will be performed to assure assumptions associated with using ANOVA are met. Analysis of Means (ANOM) methods will be used to compare means and variances across groups. These methods will be appropriate to test if any of the group means are statistically different from the overall mean or if the group standard deviations are statistically different from the root mean square error (RMSE). Tukey HSD multiple comparison procedure will be used to test for all pairwise differences among the means (Tukey 1953, Kramer 1956). This test is an exact alpha-level test if the sample sizes are the same, and conservative if the sample sizes are different (Hayter 1984).

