The primary endpoint of efficacy, the effects of the study drug, ciraparantag compared to a placebo on the reversal of anticoagulation induced by rivaroxaban, will be determined. Blood samples (2 ml) for measuring of clotting time by WBCT will be collected at the following time points:

Day 3: pre-rivaroxaban (within 1 hour prior to dosing) and post-rivaroxaban at 3.75 and post-study drug at 0.25, 0.5, 0.75, 1, 2, 4, 6, 8 and 24 hours (hrs). (Only subjects with at least 25% increase of clotting time from pre-rivaroxaban level on day 3 will be randomized). Triplicate WBCT will be done pre-rivaroxaban, post-rivaroxaban at 3.75 hrs and post-study drug at 1 hr, and median WBCT values will be derived and used for analysis in this study.

Secondary endpoints, including the PK characteristics of rivaroxaban and ciraparantag and its primary metabolite, will be assessed. A 4mL blood sample in potassium EDTA will be collected for each PK assessment of rivaroxaban. Rivaroxaban PK time points include:

Day 3: pre-rivaroxaban (within 1 hr prior to dosing), post-rivaroxaban at 3.75, 4.25, 4.5, 4.75, 5, 6, 8, 10, 12, and 28 hrs.

A 3mL blood sample with no additive (i.e. serum sample) will be collected for each PK assessment of ciraparantag and its metabolite. Ciraparantag or placebo is administered 4 hrs after the rivaroxaban dosing on Day 3. Ciraparantag and its metabolite PK time points include:

Day 3: pre-study drug (within 1 hr prior to dosing of ciraparantag or placebo), post-study drug at 0.25, 0.5, 0.75, 1, 2, 4, 6, 8 and 24 hrs.

Safety monitoring, including medical history interviews, AEs, physical examinations, vital signs, laboratory testing and electrocardiogram (ECG) will be performed.

The schedule of procedures is presented in [Table 1](#). For a detailed description of study procedures, please refer to protocol Section “STUDY PROCEDURES”.

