#### **3.1.1 Efficacy Endpoints**

The primary efficacy endpoint will be the PD assessment of clotting time by WBCT, and clotting time between placebo and treatment at 15, 30, 45 minutes or 1 hour post ciraparantag administration, on Day 3. The PD parameters will include  $E_{min}$ ,  $tE_{min}$ ,  $E_{min(0-6h)}$ ,  $tE_{min(0-6h)}$ ,  $E_{max}$ ,  $tE_{max}$ , and  $\Delta E_{max}$ .

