## 4.7 Efficacy Analyses

### 4.7.1 Primary Analysis

The efficacy endpoint will be PD assessment of clotting time by WBCT, efficacy endpoint will be summarized at observed time points and change and/or ratio from baseline values using descriptive statistics and graphical presentations. In addition, the summary by time point will include percent-of-baseline  $\leq 110\%$ ,  $\geq 125\%$ , and  $\geq 130\%$ . In addition, an additional summary of the counts and percentages of subjects with  $\leq 110\%$ , and  $\leq 115\%$  at each time point (categorical) will be produced.

Change-from-baseline and percent-of-baseline will be calculated for all efficacy endpoints. Baseline for all efficacy endpoints will be defined as the pre-rivaroxaban sample (approximately 4 hours before ciraparantag or placebo administration on Day 3).

The anticoagulant effect of rivaroxaban will be evaluated by comparing WBCT measured at pre-ciraparantag (about four hours post-rivaroxaban on Day 3) versus baseline (pre-rivaroxaban on Day 3). For the purposes of the efficacy analyses, subjects with percent-of-baseline WBCT at pre-ciraparantag  $< 125\%$  (i.e.,  $< 25\%$  increase) will be considered as rivaroxaban non-responders and excluded from all efficacy summaries and assessments.

Listings of individual efficacy variable collection times, as well as derived sampling time deviations (where applicable), will be provided.

Individual observed and baseline-adjusted values at scheduled time points and efficacy parameters will be listed and summarized by treatment. In addition, the nature of reversal of anticoagulation based on the definition of reversal of anticoagulation below using WBCT will be listed for each subject and summarized.

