#### Definition of Reversal of Anticoagulation

- Complete reversal is achieved for a treatment group if the mean WBCT is  $\leq 110\%$  of baseline at any post-baseline time point up to and including 1 hour following test

article administration. Complete reversal is achieved for a subject if WBCT is  $\leq 110\%$  of baseline at any post-baseline time point up to and including 1 hour following test article administration

- Complete and sustained reversal of anti-coagulation is achieved for a treatment group if the mean WBCT is  $\leq 115\%$  of baseline at all time points between 1 and 8 hours (inclusive) following test article administration. Complete and sustained reversal of anti-coagulation is achieved for a subject if WBCT is  $\leq 115\%$  of baseline at all time points between 1 and 8 hours (inclusive) following test article administration.

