#### Statistically Significant Complete Reversal

- Statistically significant complete reversal, relative to mean placebo WBCT, is defined as  $p < 0.05$ , (one tailed) from the comparison of means between treatment and placebo at 15, 30, 45 minutes or 1 hour post study drug administration as measured by one-way Analysis of Variance (ANOVA) at study completion. Distribution diagnostics will be performed to assure assumptions associated with using ANOVA are met. One-tailed Dunnett's test will be used for comparisons of treatment means.

Analysis of Means (ANOM) methods will also be used to compare means and variances across groups. These methods will be appropriate to test if any of the group means are statistically different from the overall mean or if the group standard deviations are statistically different from the root mean square error (RMSE).

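### The dose-versus-placebo test is a one-way ANOVA with no named response scale and no pre-drug WBCT covariate: an avoidable loss of precision, chiefly for partial-effect doses

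*SAP*

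**What the plan says.** SAP 4.7.1, under Statistically Significant Complete Reversal, defines that outcome as one-tailed p<0.05 from a "comparison of means between treatment and placebo at 15, 30, 45 minutes or 1 hour post study drug administration". The model is given in the words "as measured by one-way Analysis of Variance (ANOVA) at study completion", and Protocol 9.8 has the same one ("as measured by one-way Analysis of Variance at study completion"). The SAP applies one-tailed Dunnett across doses, and SAP 4.11 records that this replaced Tukey HSD.

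The response scale is not stated:
- The test sentence refers only to mean placebo WBCT.
- SAP 3.1.1 describes "clotting time between placebo and treatment at 15, 30, 45 minutes or 1 hour post ciraparantag administration", again without a scale.
- SAP 4.7.1 says "Change-from-baseline and percent-of-baseline will be calculated for all efficacy endpoints" but assigns neither to the test.
- The reversal definition just before the test ("Complete reversal is achieved for a treatment group if the mean WBCT is" ≤110% of baseline) uses mean WBCT for a percent-of-baseline quantity.

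On the pre-drug values, SAP section 3 states: "Triplicate WBCT will be done pre-rivaroxaban, post-rivaroxaban at 3.75 hrs and post-study drug at 1 hr", with the median analysed. The pre-rivaroxaban value is the efficacy baseline. The 3.75 h value has four uses: the 25% entry gate, the description of rivaroxaban's effect, the inter-observer analysis in SAP 4.7.2, and the rule that subjects below 125% of baseline "will be considered as rivaroxaban non-responders and excluded from all efficacy summaries and assessments". Neither value is a covariate in any WBCT model.

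**The concern.** Subjects differ in baseline clotting time and in how far rivaroxaban prolongs it. Both are measured, with replication, before randomised drug, so adjusting for them cannot introduce bias and would normally shrink the error term. If the response is observed WBCT, the test uses neither value. If it is percent-of-baseline, the first value is largely used already as the divisor, and the 3.75 h value is left unused.

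With 12 subjects per dose against 16 pooled placebo, precision matters most for doses with a partial effect. The unnamed scale is a further weakness. Two analysts could follow this SAP and test different quantities, in a single-blind study where a group including the investigator and sponsor reviews PD data between cohorts (Protocol 5.9).

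**Working it through.** **Inputs from the documents.** Four cohorts of 16 at 3:1 give 4 × 12 active and 4 × 4 = 16 pooled placebo, 64 in all (SAP 3.4, 3.5). The test is at 5%, one-tailed, with Dunnett. No SD, effect size, correlation or power is given (SAP 3.4), so there is no plan figure to reproduce, and every R², CV and effect below is an assumption. All power figures are per dose at one time point.

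**Step 1, analytic.** Error df are 64 − 5 = 59, or 57 with two covariates. The Dunnett cut-offs are 2.228 and 2.229. In SD units, SE = √(1/12 + 1/16) = 0.382. With covariates the SE is multiplied by √((1 − R²) × 59/57), which is 0.910, 0.851 and 0.719 at R² 0.2, 0.3 and 0.5. Noncentral-t power is:

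| True effect | ANOVA | R² 0.2 | R² 0.3 | R² 0.5 |
|---|---|---|---|---|
| 0.8 SD | 45.2% | 53.2% | 59.4% | 75.1% |
| 1.2 SD | 81.7% | 88.6% | 92.5% | 98.2% |
| 1.5 SD | 95.3% | 98.0% | 99.0% | 99.9% |

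At R² = 0 the factor is √(59/57) = 1.017, and power at 0.8 SD falls from 45.2% to 43.8%, a cost of 1.4 points. Break-even is at R² = 1 − 57/59 = 0.034.

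**Step 2, by response scale.** Simulation of 10,000 trials assumed a mean rise of 40% and the 25% gate applied to measured medians. Reversal was 10% on placebo and 20/35/50/80% by dose. Across three settings, the log SD of baseline and of rise was 0.10/0.06/0.04 and reading noise was 0.06/0.08/0.08. The 35% dose then averages 128/127/126% of baseline and placebo 140/138/137%.

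| Response and model | Power, 35% dose | Power, 50% dose |
|---|---|---|
| Raw WBCT, ANOVA | 39/50/60% | 77/89/95% |
| Percent-of-baseline, ANOVA | 69/55/57% | 98/92/92% |
| Log ANCOVA, both covariates | 87/61/62% | 99.9/96/97% |

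For the 35% dose, the ANCOVA gain over percent-of-baseline is 87 − 69 = 18, 61 − 55 = 6 and 62 − 57 = 5 points. Over raw WBCT it is 48, 11 and 2. Against the log of percent-of-baseline (67/52/53%) it is 20, 9 and 9. At the 80% dose (108% of baseline), power is 99.8–100% under every analysis. Familywise error at one time point was 4.4–5.2% for raw WBCT, percent-of-baseline and the two-covariate ANCOVA.

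**Step 3, second set of assumptions.** A further simulation of 1,500 trials per scenario used between-subject CV 10–20%, measurement CV 5–8% and rise SD 12–15 points:

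| Reversal | Raw WBCT | Percent-of-baseline | ANCOVA, both covariates, arithmetic scale |
|---|---|---|---|
| 20% | 10–22% | 29–50% | 30–56% |
| 30% | 19–45% | 55–84% | 61–92% |

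Setting by setting, the gain over percent-of-baseline runs from 0.8 points (28.9% to 29.7%) to 8.4 points (83.5% to 91.9%). Like for like on the log scale, covariates gain from 1.0 (22.1% to 23.1%) to 11.9 points (76.6% to 88.5%). In the noisiest setting, however, the log ANCOVA falls below arithmetic percent-of-baseline: 23.1% against 28.9% at 20% reversal, and 54.3% against 55.2% at 30%. Part of that arithmetic-scale advantage is not real precision. Strongly reversed doses have smaller absolute spread and pull down the pooled error used for the placebo comparison.

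**Step 4, a dose at exactly 110% with placebo at 130%.** The log difference is ln(130/110) = 0.167. At CV 10% this is about 1.67 SD, and unadjusted power is 98%. At CV 15% it is about 1.12 SD, and power is 76%, rising to 84/88/97% at R² 0.2/0.3/0.5. A dose at the threshold is therefore at risk only if spread is wide or placebo has drifted down.

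**The case against.** The strongest reply is that the test is named for complete reversal, not partial effect, and doses that truly reverse are usually detected without covariates. A reader might infer that the study needs its partial-effect dose to beat placebo. Protocol 5.9 does not say so: it asks for a dose with partial or no effect, and a non-significant dose meets that aim. Escalation follows the mean criterion in the Protocol synopsis, not this test. All of this stands.

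A second reply also stands and changes the fix. The SAP attaches the complete-reversal label to any dose with p<0.05. In Step 2 a dose at 126–128% of baseline earns it 69/55/57% of the time on percent-of-baseline and 87/61/62% with ANCOVA. Extra power alone would mislabel more doses.

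Third, a reader might infer that the plan tests observed WBCT, where the loss is usually largest. The documents do not settle that. SAP 3.1.1 gives no scale, and the adjacent reversal definition favours percent-of-baseline at least as naturally. On that reading naming the scale is the larger part of the remedy in most settings, and the covariate gain is modest.

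Finally, one-way ANOVA with Dunnett is a recognised method and the ANCOVA is a choice of efficiency. That is fair. The case for it is that the data are already collected and the downside is small.

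**Conclusion.** The point holds as one of efficiency and pre-specification, worth considering rather than essential. The missing scale and missing covariates are plain from the text. The size is not. Under assumed variances, adding both covariates gains roughly 1 to 20 points over percent-of-baseline for partial-effect doses, with the upper end coming from one setting with wide between-subject spread. The gain is usually larger against raw WBCT. In one noisy setting the log-scale model did up to 6 points worse than arithmetic percent-of-baseline. For doses near full reversal the gain is almost nothing unless spread is wide. The 25% entry gate narrows the range of the 3.75 h value and may reduce its usefulness.

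A reader might infer bias, an invalid test or an underpowered trial. None follows: both covariates precede randomised drug, simulated error rates at one time point are near nominal, and the plan makes no power claim. Which of the four time points decides is a separate multiplicity question that covariates do not touch.

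**What to change.** In SAP 4.7.1:
- Name the response, and identify each pre-drug value explicitly. SAP 3.5 defines baseline generally as the last value before study drug, whereas 4.7.1 uses the pre-rivaroxaban sample.
- Make the comparison an ANCOVA on log WBCT with treatment (each dose and pooled placebo) and the log pre-rivaroxaban and log 3.75 h medians as covariates. Apply one-tailed Dunnett to the adjusted means and report geometric LS ratios versus placebo.
- Keep the common-slope model as primary whatever a treatment-by-covariate check shows, and keep the one-way ANOVA as a sensitivity analysis.
- Leave the reversal criteria unchanged. Use the label of statistically significant complete reversal only when p<0.05 and the ≤110% mean criterion are both met. Otherwise report a significant difference from placebo.
- Deal with the four time points separately.

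The cost is SAP wording and an entry in SAP 4.11, with no new data and two of 59 error df. The test would be on the log scale beside a criterion on the arithmetic scale. The entry should be dated and should acknowledge the between-cohort PD review. The SAP revision history says version 4.0 took updates from the SAP for PER977-02-011, so alignment with that plan, which is not among these documents, should be checked.

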5.9 Dose Escalation/De-Escalation

Review of pharmacodynamic, AEs, clinical laboratory tests, and ECG data will be conducted by a group that includes the Principal Investigator, Medical Monitor(s), and representative(s) of the Sponsor. The group will be responsible for the decision to expand a given dose cohort, escalate (or de-escalate) to a different dose from the planned dose, or stop the study. All meetings will be documented with minutes.

The goal of the study is to explore the dose range of ciraparantag that reverses the anticoagulation induced by therapeutic doses of rivaroxaban at steady state. The study is intended to establish a dose of ciraparantag that fully reverses steady-state rivaroxaban, to evaluate at least one dose above the reversal dose to establish a therapeutic index, and at least one partial or no effect dose.

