### **2.2 Secondary Objectives**

The secondary objectives of this study are:

[figure not shown]
- To evaluate the safety and tolerability of ciraparantag 60 mg, 120 mg, 180 mg, and 30 mg, and additional cohorts if necessary, administered 4 hours after 20 mg rivaroxaban administration at steady state.
- To assess the PK characteristics of rivaroxaban and ciraparantag and its primary metabolite, 1,4-bis(3-aminopropyl) piperazine (BAP).

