### 3 Study Design and Methods

This is a Phase 2, prospective, randomized, single-blind, placebo-controlled study to assess the efficacy of ciraparantag administered to healthy volunteers by measuring clotting times using WBCT. All subjects will undergo screening up to 36 days prior to enrollment. Randomization will take place on Day 3 after administration of rivaroxaban. Subjects will be enrolled sequentially into up to four cohorts, and a minimum of 2 days between completion of treatment in one cohort and initiation of treatment in the subsequent cohort is required.

Subjects (n=16 per cohort) will be randomized in a 3:1 ratio to receive ciraparantag or placebo (saline for injection) (Figure1).

Figure 1 Dose Schema

All subjects will receive a single dose of 20 mg rivaroxaban in the morning on Days 1-3. Study drug will be administered only to those subjects who have a minimum increase in clotting time of 25% (as measured by WBCT) above Day 3 pre-rivaroxaban levels at the pre-study drug time point on Day 3 (i.e., 3.75 hours post rivaroxaban). Any subject who does not have a minimum increase in clotting time of 25% above Day 3 pre-rivaroxaban levels at the pre-study drug time point on Day 3 will be discontinued from the study and replaced. At 4 hours following rivaroxaban a single IV dose of study drug (ciraparantag or placebo) will be administered, all doses of study drug will be administered by IV injection over a minimum of 10 minutes.

Individual subjects may only participate in one dose cohort of this study. Any subject who discontinues prior to completion for reasons other than an AE will be replaced and the replacement subject will receive the same treatment as the original subject. Subjects who discontinue due to an AE that precedes administration of study drug may be replaced at the discretion of the Sponsor. Only those subjects who discontinue due to AEs that follow administration of study drug (ciraparantag or placebo) will not be replaced.

Expectation of the total duration of the study is approximately 3 months. Individual subject participation is approximately 50 days inclusive of screening and follow-up. Subjects enrolled will spend up to four nights admitted to an in-patient facility.

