#### **4.11 Changes from Pre-Specified Analyses**

The definition of concomitant medication is changed from “any medication other than the trial product that is taken during the trial including the screening period” in the protocol to “any medication other than the trial product that is taken on or after the first dose of rivaroxaban” in the analysis planned for this study.

In the statistical analysis of complete reversal, Tukey HSD multiple comparison procedure was replaced by one-tailed Dunnett’s test for comparison of treatment and placebo means.

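### Step-down Dunnett would detect a weaker dose more often than the SAP's single-step Dunnett at the same familywise 5% per time point, but it needs a rule for time points and variances with it

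*SAP*

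**What the plan says.** SAP 4.7.1, under Statistically Significant Complete Reversal, sets a one-tailed 5% criterion for dose against placebo, by one-way ANOVA, "at 15, 30, 45 minutes or 1 hour post study drug administration". A one-tailed Dunnett's "test will be used for comparisons of treatment means". SAP 4.11 records only that "Tukey HSD multiple comparison procedure was replaced by one-tailed Dunnett"'s test. Neither place mentions a step-down or closed procedure, a dose order, or an adjustment across the four times. The same part of 4.7.1 plans analysis-of-means methods to compare group means and variances, but gives no consequence if the variances differ.

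Four doses are planned: "ciraparantag 60 mg, 120 mg, 180 mg, and 30 mg, and additional cohorts if necessary" (SAP 2.2). SAP 3 states: "Subjects (n=16 per cohort) will be randomized in a 3:1 ratio to receive ciraparantag or placebo". Placebo subjects are pooled across cohorts (SAP 3.5; Protocol 9.1). Protocol 5.9 says that the study should find a fully reversing dose, test at least one dose above it, "and at least one partial or no effect dose".

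**The concern.** Single-step Dunnett holds every dose to the critical value for four comparisons, even after the other doses have been declared different from placebo. Step-down Dunnett lowers the bar as doses are rejected. It rejects everything that the single-step test rejects, and sometimes more.

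The loss from single-step is greatest for a weak dose beside several strong ones, which is the pattern the dose plan aims for. What is at stake is that a real partial effect may be reported as not different from placebo. There was no formal sample-size calculation (SAP 3.4), so nothing shows that power can be spared. The usual reason to keep single-step is its matching simultaneous confidence intervals, and the SAP text plans none for these comparisons.

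**Working it through.** The documents state no power figure, so there is none to reproduce.

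**Inputs from the documents.** There are four doses and 16 subjects per cohort at 3:1, so 12 per dose and 4 × 4 = 16 pooled placebo. Error df = 64 − 5 = 59. The correlation between two dose-placebo contrasts is 12/(12 + 16) = 0.429. **Assumed:** effects in SD units, and equal variances unless stated otherwise.

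**Critical values** (one-sided 5%, multivariate t):

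| Doses still in the family | 4 | 3 | 2 | 1 |
|---|---|---|---|---|
| Critical value | 2.228 | 2.121 | 1.963 | 1.671 |

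Single-step uses 2.228 for every dose. Step-down uses the four values in turn, from the largest statistic to the smallest, and stops at the first failure.

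**Hand check at 0.8 SD.** The standard error is √(1/12 + 1/16) = 0.382 SD, so the expected statistic is 0.8/0.382 = 2.095. By normal approximation, single-step power is Φ(2.095 − 2.228) = 45%. If the other three doses are always rejected, step-down power is Φ(2.095 − 1.671) = 66%.

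**Simulated power for the weaker dose** (200,000 trials per row):

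| Weaker dose | Other three | Single-step | Step-down | Gain (points) |
|---|---|---|---|---|
| 0.5 SD | 2 SD | 18.7% | 36.3% | 17.6 |
| 0.6 SD | 2 SD | 26.4% | 46.5% | 20.1 |
| 0.8 SD | 2 SD | 45.3% | 66.5% | 21.2 |
| 1.0 SD | 2 SD | 65.6% | 82.8% | 17.2 |
| 0.75 SD | 1 SD | 40.1% | 54.0% | 13.9 |
| 0.75 SD | no effect | 40.1% | 40.2% | 0.1 |

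**Familywise error at one time point** (effective doses at 2 SD, 400,000 trials):

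| Inert doses | Single-step | Step-down |
|---|---|---|
| 4 | 5.0% | 5.0% |
| 3 | 3.9% | 5.0% |
| 2 | 2.8% | 5.0% |
| 1 | 1.5% | 5.1% |

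**Any of four time points, unadjusted.** With all doses inert, the chance of a false claim is about 8%, 11% or 15% for an assumed between-time correlation of 0.95, 0.8 or 0.5, the same for both procedures. With one inert dose beside three at 2 SD, it is 2.4%, 3.6% or 4.8% with single-step, and 7.6%, 10.5% or 14.5% with step-down.

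**Unequal variances.** Let the inert-dose and placebo SDs both be r times the SD of the three reversed arms. The pooled variance is (33 + 26r²)/59, where 33 = 3 × 11 and 26 = 11 + 15.
- r = 1.5: √(91.5/59) = 1.245, and 1.245/1.5 = 0.830, so the inert-dose standard error is understated by 17%.
- r = 3: √(267/59) = 2.127, and 2.127/3 = 0.709, so it is understated by 29%.

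Over this range the inert-dose error at one time point is about 9–12% with step-down and 3.5–6.2% with single-step. If only the placebo SD is inflated, the understatement is 7–17%. If only the inert-dose SD is inflated, it is 15–33%.

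**The case against.** Single-step Dunnett is a legitimate choice. It controls error at each time point under equal variances, suits comparisons with a control better than Tukey, and allows simultaneous confidence limits. The SAP text plans no such limits, but the table shells are a separate document (SAP 4.10) that could. All this stands, so the point is one of efficiency.

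A reader might infer that step-down would help to separate a reversing dose from a partial one. The documents do not support that. Reversal is classified by the 110% and 115% of baseline rules (SAP 4.7.1; Protocol 9.8), and the Protocol Synopsis ties dose escalation to the sustained 115% criterion, not to a p-value. If the p-value alone were taken as the definition of statistically significant complete reversal, more power would simply give that label to more partial doses.

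A reader might also infer that the swap leaves the trial's false-claim rate at 5%. That is true only at one time point with equal variances. Under the any-of-four-times rule, or under a pooled variance with unequal SDs, step-down spends the slack that single-step leaves for a lone inert dose. This objection stands, and it determines what the fix must contain.

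Finally, the gain rests on assumed effects, and its upper range needs three strongly effective doses.

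**Conclusion.** The point holds as lost efficiency, not as an invalid test. At one time point with equal variances, step-down Dunnett keeps the familywise 5% and gains power wherever other doses work: about 17–21 points for a dose at 0.5–1.0 SD beside three at 2 SD, about 14 points at 0.75 SD beside three at 1 SD, and essentially none if no other dose works. These sizes assume 64 evaluable subjects, four doses and effects in SD units that the documents do not supply. The test named in the SAP is not printed as single-step; that is the ordinary reading of an unqualified Dunnett's test.

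The unadjusted choice among four times already gives a worst-case error of about 8–15% (assumed correlation 0.95 to 0.5). Step-down neither causes nor cures this. It does remove the protection that single-step happens to give a single inert dose, so the change is worth making only together with a rule for time points and variances.

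**What to change.** In SAP 4.7.1, replace the Dunnett sentence with: *One-tailed step-down Dunnett (closed testing) at familywise 5% will be used to compare each dose with pooled placebo.* Update SAP 4.11 to match. In the same revision:

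- Name one primary time point, or specify an adjustment across 15, 30, 45 minutes and 1 hour.
- Prespecify arm-specific variances for these comparisons. Do not let the analysis-of-means check trigger them, because a preliminary-test rule has unstated error properties at 12 per arm. Confirm the chosen version by simulation at these sample sizes, which the calculations here do not cover.
- State that the p-value is a comparison with placebo, and that the 110% and 115% rules classify reversal.

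The cost is a few SAP sentences and a little programming, with no added subjects, visits or samples. Matching simultaneous confidence intervals are lost; single-step limits can still be shown descriptively.
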